5.7.3.3 Criteria for CC-486 Discontinuation

CC-486 needs to be permanently discontinued for any of the following:

- Any life-threatening adverse reaction
- Anaphylactic-like reaction related to CC-486 administration
- Necrotising fasciitis
- Any criteria/event listed in section 5.5 or 5.7.3

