5.5 Study Treatment Discontinuation

By default, subjects are treated until progressive disease as per irRECIST (Appendix 2) when study treatment must be discontinued. CA-125 increases should not be used to declare disease progression and/or study treatment discontinuation (refer to section 6.4.6.2).

In Part A and in Arm A of Part B, in case there is a need to permanently discontinue one of the study drugs (whichever the reason), the other one will also be discontinued (i.e. monotherapy with CC-486 or with pembrolizumab is not allowed in Part A and in Arm A of Part B).

The Investigator will also discontinue study treatments if any of the following conditions is met:

- Intercurrent illness or a change in subject's condition or unacceptable toxicity (see section 5.7) that warrants study treatment discontinuation according to Investigator judgment
- Any event, condition, criterion which would warrant discontinuation of pembrolizumab or CC-486 as per section 5.7.
- Any event, condition, reason which would warrant pembrolizumab or CC-486 to be held for more than the maximum acceptable delay as per section 5.7.1.
- Subject completed 24 months of uninterrupted treatment with pembrolizumab or 35 administrations of pembrolizumab, whichever is later (*Note: 24 months is calculated from the date of first pembrolizumab dose*).
- Need for additional local and/or systemic non-protocol anticancer therapy or subject receives non-protocol anticancer therapy at any time during the study treatment
- Subject's decision to withdraw study treatments
- Lost to follow up
- Death
- Pregnancy
- Investigator's decision
- Discontinuation of the study by the sponsor

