5.7 Treatment Schedule Adjustments and Adverse Events Management

5.7.1 General Rules

Regular assessment and monitoring of AEs is required throughout study treatment period and at least up until the End of Treatment visit (refer to section 7.1.1).

Toxicity will be assessed utilizing the National Cancer Institute Common Terminology Criteria for Adverse Events (NCI CTCAE) v4.03. For toxicities not specifically listed in the NCI CTCAE, the following grading will apply for assessing severity:

- Grade 1: Mild
- Grade 2: Moderate
- Grade 3: Severe
- Grade 4: Life-threatening
- Grade 5: Death related to AE

Subjects will be instructed to notify their physician immediately for any and all toxicities. Assessment of causality (chronology, confounding factors, concomitant medications, diagnostic tests, and previous experience with the study treatment) should be conducted by the Investigator prior to dose modification and/or delay whenever possible. As a general approach, it is suggested that all AEs be managed with supportive care at the earliest signs of toxicity and before delaying/reducing study drugs, when possible and if clinically appropriate.

All dose modifications should be based on the AE requiring the greatest modification and should be properly documented in source documents. Investigators may take a more conservative approach than the guidelines outlined in the protocol on the basis of clinical judgment that this is in the best interest of the subject.

In case a delay/withhold of one study drug is required, treatment with the other drug may continue according to the protocol schedule if clinically appropriate (applicable for Part A and Arm A of Part B).

Maximum acceptable delays due to adverse events related to study drug(s) are:

- For pembrolizumab: 12 weeks after prior dose of pembrolizumab
- For CC-486: the maximum number of days that dose may be withheld due to toxicity before a subject is permanently discontinued from CC-486 is 14 days (not comprising treatment off-period)

If due to an adverse event related to study drug(s) it is required to delay study treatment for more than the maximum acceptable period, then study treatment should be permanently discontinued and subject should undergo the End of Treatment visit.

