Dosing interruptions/delays of one or both study drugs with a maximum duration of 21 days are permitted in the case of medical/surgical events or logistical reasons unrelated to study treatments (e.g. elective surgery, unrelated medical events, subject vacation and/or holidays). Subjects should be placed back on study therapy within 21 days of the scheduled interruption, unless otherwise discussed with the Medical Monitor.

In Part A and in Arm A of Part B, in case there is a need to permanently discontinue one of the study drugs (whichever the reason), the other one will also be discontinued (i.e. monotherapy with CC-486 or with pembrolizumab is not allowed in part A and in Arm A of Part B).

General guidelines on dose delay and modifications for each of the study drugs are detailed in the following subsections.

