Nephritis and Renal dysfunction	Grade 2	Withhold	Administer corticosteroids (prednisone 1-2 mg/kg or equivalent) followed by taper.	Monitor changes of renal function
	Grade 3 or 4	Permanently discontinue		

Immune-related AEs	Toxicity grade or conditions (CTCAEv4.0)	Action taken to pembrolizumab	irAE management with corticosteroid and/or other therapies	Monitor and follow-up
Myocarditis	Grade 1 or 2	Withhold	Based on severity of AE administer corticosteroids	Ensure adequate evaluation to confirm etiology and/or exclude other causes
	Grade 3 or 4	Permanently discontinue		
Stevens Johnson Syndrome	Any grade	Permanently discontinue	Refer the patient for specialized care for assessment and treatment.	Refer the patient for specialized care for assessment and treatment.
Toxic Epidermal Necrolysis	Any grade	Permanently discontinue	Refer the patient for specialized care for assessment and treatment.	Refer the patient for specialized care for assessment and treatment.
All other immune-related AEs	Intolerable/persistent Grade 2	Withhold	Based on type and severity of AE administer corticosteroids	Ensure adequate evaluation to confirm etiology and/or exclude other causes
	Grade 3	Withhold or discontinue based on the type of event. Events that require discontinuation include and not limited to: Guillain-Barre Syndrome, encephalitis		
	Grade 4 or recurrent Grade 3	Permanently discontinue		

1. Withhold or permanently discontinue pembrolizumab is at the discretion of the investigator or treating physician.
 
NOTE:
 
For participants with Grade 3 or 4 immune-related endocrinopathy where withhold of pembrolizumab is required, pembrolizumab may be resumed when AE resolves to ≤ Grade 2 and is controlled with hormonal replacement therapy or achieved metabolic control (in case of T1DM).
				

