5.7.3 CC-486

5.7.3.1 Dose Levels

Refer to Table 3: CC-486 dose levels for guidance on dose reduction levels for each schedule. Dose reductions will be allowed from the original start dose except in Schedule 1 where no dose reductions are allowed.

Re-escalation to the higher dose level is not permitted once dose has been reduced due to toxicity with the only exception of cases considered in Table 4.

Table 3: CC-486 dose levels

Dose levels	Schedule 1	Schedule 2	Schedule 3	Schedule 4
Dose level 0 (Starting dose)	100 mg q.d. D1-21	100 mg BID D1-21	300 mg q.d D1-14	300 mg q.d D1-21
Dose level -1	No dose reduction allowed. Discontinue.	100 mg q.d	200 mg q.d.	200 mg q.d.
Dose level -2	Not applicable	Discontinue	100 mg q.d	100 mg q.d
Need for additional dose reduction	Not applicable	Not applicable	Discontinue	Discontinue

q.d.: once a day; BID: twice a day

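### Table 5 directs re-challenge in Schedules 2 to 4 after a recovered grade 4 toxicity not listed in CTCAE, although Sections 5.7.3.3 and 5.5 require a permanent stop

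*Protocol*

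**What the plan says.** Four parts of the protocol bear on the same event.

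- **Section 5.7.1** sets a fallback severity scale: "For toxicities not specifically listed in the NCI CTCAE, the following grading will apply for assessing severity". On that scale the fourth step reads "Grade 4: Life-threatening".
- **Section 5.7.3.3** lists the mandatory grounds for permanent CC-486 discontinuation. The first is "Any life-threatening adverse reaction". There is no exception for events that recover. The last item on the list brings in the stopping criteria found elsewhere in 5.5 and 5.7.3.
- **Section 5.5** obliges the investigator to stop study treatment when any one of its listed conditions is met. One of them is "Any event, condition, criterion which would warrant discontinuation of pembrolizumab or CC-486 as per section 5.7". For Part A and for Arm A of Part B it adds: "in case there is a need to permanently discontinue one of the study drugs (whichever the reason), the other one will also be discontinued".
- **Table 5 (Section 5.7.3.2)** has a catch-all row for grade 3 or 4 non-hematologic toxicities not named elsewhere in the table. CC-486 is held. If the event returns to grade 1 or below within 7 days, the dose goes down one level where Table 3 permits, and treatment resumes. Schedule 1 stops instead. CC-486 also stops if no level is left, if there is no recovery by 7 days, or if the event comes back at equal or higher severity on the lower dose.

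Schedule 1 differs because of Section 5.7.3.1: "Dose reductions will be allowed from the original start dose except in Schedule 1 where no dose reductions are allowed".

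**The concern.** Table 5 names grade 4 and gives it a route back to treatment. For a toxicity graded on the 5.7.1 scale, grade 4 is life-threatening by definition, so the same event also meets the first ground in 5.7.3.3. A site working from the table would re-expose a subject whom 5.7.3.3 and 5.5 require to stop. A site working from 5.7.3.3 would end both drugs.

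In Part A the choice also affects evaluability. Section 3.3 requires two completed CC-486 cycles, and under Section 3.1 a subject who stops earlier is replaced. What is at stake is therefore the subject's safety and her evaluability. The efficacy and safety analysis sets are not at stake.

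**Working it through.** The plan has no figure to reproduce. The check sets the texts side by side for one event and then counts what each allows.

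**Event considered:** related to CC-486, not immune-related, not hematologic, not listed in CTCAE, grade 4, back to grade 1 or below within 7 days.

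1. Not listed in CTCAE, so the 5.7.1 scale applies, and grade 4 means life-threatening.
2. Related to CC-486, so it is an adverse reaction. 5.7.3.3 then requires a permanent stop of CC-486, and 5.5 extends the stop to pembrolizumab.
3. Not hematologic and not one of the toxicities named in Table 5, so the catch-all row applies. With recovery inside 7 days in Schedule 2, 3 or 4 and a level left, that row says to reduce and re-challenge.
4. Steps 2 and 3 cannot both be carried out.

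**Why the restrictions are needed**

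- *Immune-related events drop out.* In Table 1 an immune-related event without its own row permanently stops pembrolizumab at "Grade 4 or recurrent Grade 3", and 5.5 then stops CC-486.
- *Schedule 1 drops out of the Table 5 conflict*, because the catch-all row itself orders a stop there.
- *Subjects with no level left drop out*, because both texts stop them.

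**Re-challenges allowed after a qualifying event** (dose levels from Table 3)

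| | Schedule 1 | Schedule 2 | Schedule 3 | Schedule 4 |
|---|---|---|---|---|
| Start, mg/day | 100 | 200 | 300 | 300 |
| Levels below start | 0 | 1 | 2 | 2 |
| First lower dose | none | 100/200 = 50% | 200/300 = 67% | 200/300 = 67% |
| Second lower dose | none | none | 100/300 = 33% | 100/300 = 33% |
| Maximum under Table 5 | 0 | 1 | 2 | 2 |
| Maximum under 5.7.3.3 | 0 | 0 | 0 | 0 |

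The second re-challenge in Schedules 3 and 4 can arise in two ways. It can follow a different event. It can also follow the same event returning at a lower grade, because Table 5 stops CC-486 only on recurrence at equal or higher severity. A grade 4 event that returns at grade 3 is still in the row and is less severe than before.

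**Example.** A Schedule 4 subject has such an event in Cycle 1 and recovers to grade 1 in 5 days. Table 5 resumes CC-486 at 200 mg daily: 21 × 2 = 42 tablets per full cycle instead of 21 × 3 = 63. Under 5.7.3.3 and 5.5 both drugs end, and in Part A she is replaced.

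**CTCAE-listed grade 4 events.** For these, 5.7.1 does not equate grade 4 with life-threatening. The only definition in the protocol is the footnote to 7.1.3, which requires that the subject was in immediate danger of dying when the event occurred. If 5.7.3.3 is read with that meaning, events without that danger follow Tables 4 and 5, events with it follow 5.7.3.3, and both texts can be obeyed. This covers:

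- the Table 5 rows;
- grade 4 neutropenia in Table 4, which resumes at the same dose in all schedules, including Schedule 1, after recovery within 7 days;
- grade 4 thrombocytopenia in Table 4, which resumes one level lower in Schedules 2 to 4 after recovery within 7 days with a level left.

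**Analysis sets.** ITT membership depends on enrollment or randomization and Safety membership on one dose (Protocol 8.1; SAP 3.1.1 and 3.1.2), so neither depends on the path taken. The Step 1 toxicity limits in Section 3.3 count her event on either path. Only membership of the SAP's Evaluable Population (3.1.3) can differ, through the two-cycle condition. The SAP bases its efficacy analyses on ITT and its safety analyses on the Safety population.

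**The case against.** The strongest reply is that the protocol already gives the answer. Section 5.5 is mandatory and needs only one condition to be met. Section 5.7.3.3 is also mandatory, and its last item shows that the list adds to the stops in the tables. The column in Table 5, by contrast, is headed as a recommendation, and 5.7.1 lets investigators be more cautious than the guidance. The natural reading is to follow the table unless a mandatory stop applies.

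Most of this stands. A reader might infer that the protocol is deadlocked, with nothing to favor either rule. The documents do not support that, because their mandatory wording favors the stop. What remains is that the table gives an explicit contrary instruction for grade 4 and does not refer to 5.7.3.3. The other candidate tie-breakers do not settle it:

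- The 5.7.1 rule about the event needing the greatest modification ranks different events. It does not rank two rules for one event.
- The freedom to be more conservative permits a stop without requiring it.
- "General guidelines on dose delay and modifications for each of the study drugs are detailed in the following subsections" introduces all the later subsections, 5.7.3.3 among them, so it does not place the tables below the stop list.
- The recommendation column itself contains mandatory stops, for instance for recurrent neutropenia in Table 4, so its heading does not separate advice from rule.

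A reader might also infer that every grade 4 resumption in Tables 4 and 5 contradicts 5.7.3.3. That does not follow either, because CTCAE-listed events can be reconciled through the 7.1.3 definition.

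It is also fair to say that the certain case is narrow, that the documents name no toxicity that fits it, and that 5.5 separately lets the investigator stop for unacceptable toxicity.

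**Conclusion.** The inconsistency is real but narrow. For a CC-486-related, non-immune, non-hematologic grade 4 toxicity outside CTCAE that recovers within 7 days, in Schedules 2 to 4 with a level left, Table 5 instructs re-challenge where 5.7.3.3 and 5.5 require both drugs to stop. The stop is the better reading. The size per subject is up to 1 re-challenge in Schedule 2 and up to 2 in Schedules 3 and 4, against 0. In Part B the conflict arises only if one of those schedules is chosen. If Schedule 1 is chosen, only the missing cross-reference for grade 4 neutropenia remains.

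Two assumptions underlie this. An adverse reaction in 5.7.3.3 is taken to be an adverse event judged related to CC-486, since that section does not define the term. Life-threatening is taken to have the 7.1.3 meaning for CTCAE-listed events. The documents give no frequency, so no number of affected subjects is claimed. This is a minor safety clarification.

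**What to change.** - Add a note under Tables 4 and 5 that 5.7.3.3 prevails, so that the grade 4 hold-and-resume instructions apply only to events that are not life-threatening.
- In 5.7.3.3, define life-threatening as the meaning in the 7.1.3 footnote, plus grade 4 on the 5.7.1 scale for toxicities that CTCAE does not list. Asymptomatic grade 4 blood counts then stay under Table 4.

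This takes two or three sentences and no new procedures. It could go into any amendment made before Part B, which Section 3.2 already allows for. The cost is that a subject who would have been re-challenged under the table stops both drugs and, in Part A before two CC-486 cycles are complete, is replaced.

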6. STUDY VISITS AND ASSESSMENTS

6.1 Subject Inclusion

6.1.1 Informed Consent

Prior to any study-specific screening evaluation, the subject or legally acceptable representative (if applicable per local regulation) will be informed of the nature of the study and will be given pertinent information as to the intended purpose, possible benefits, and possible adverse experiences. The procedures and possible hazards to which the subject will be exposed will be explained. A legally acceptable representative is an individual or other body authorized under applicable law to consent, on behalf of a prospective subject, to the subject's participation in the study.

An approved PICF will then be read and signed by the subject (or legally acceptable representative if applicable) and, when required, a witness, and the Investigator or a person designated by the Investigator, as per local regulations. The subject will be provided with an original copy of the signed PICF.

The subject may partially or completely withdraw from the study at anytime without prejudicing future medical treatment. In any case, the type and extent of withdrawal should be documented on the initial informed consent form, and must be dated and signed by the subject and by the Investigator.

If a potential subject or legally acceptable representative is illiterate or visually impaired, the Investigator must provide an impartial witness to read the PICF to the subject and must allow for

questions. Thereafter, both the subject or legally acceptable representative and the witness must sign the PICF to attest that informed consent was freely given and understood.

The PICF will include a statement by which the subject allows the sponsor's duly authorized personnel, the Ethics Committee (IRB/IEC), and the regulatory authorities to have direct access to its data that will be processed according to the confidentiality regulations.

If important new information becomes available that may be relevant to the subject's consent and willingness to continue participation in the study, the PICF will be revised and submitted to IRB/IEC for approval/favorable opinion. The new information will be then discussed with the subject in a timely manner and if she agrees to continue participation in the study, the revised PICF will be signed and dated and the subject will receive an original copy.

In line with each country's applicable regulations, the source should also support the documentation of the consent process, for each subject.

Both parts of this study have an optional component described in the PICF, with a consent section dedicated to this optional component. If a subject opts not to participate in the optional portion, this in no way affects the subject's ability to participate in the main research study.

6.1.2 Registration, Enrollment/Randomization and Treatment Assignment

6.1.2.1 Part A

The following steps for registering and enrolling a subject are chronologically performed:

1. The subject must provide written informed consent prior to performing any study specific procedure not considered standard practice by the institution.
2. The site will ask TRIO for subject's registration immediately after signature of PICF. A unique registration number will be assigned to each subject in the study.
3. The site will proceed to perform the screening procedures according to the Schedule of Assessments and section 6.4. Upon completion of screening procedures, the Investigator or his/her delegate will check if the subject meets all eligibility criteria:
 - Subjects who do not meet all eligibility criteria: sites will have the screen failure form completed in the eCRF with corresponding reason for screen failure captured.
 - Subjects who meet all eligibility criteria: sites will enter the screening data in the eCRF which will be reviewed centrally by TRIO. After the review of the eligibility criteria, TRIO may address, if necessary, some discrepancies that will have to be answered by the site. Once the eligibility central review is completed and discrepancies have been resolved (if applicable) TRIO will provide the confirmation that the subject is eligible and the site will be able to move forward with the subject's enrollment in the eCRF. The site will receive a confirmation of enrollment. If the subject is deemed not eligible following the central eligibility review, the site will be asked to report the screen failure reason in the eCRF.
4. Subjects will be assigned to a cohort in the order they are enrolled in the study. Subjects enrolled in Part A must start study treatment within 3 days of enrollment.

A cohort will remain open to accrual until five subjects treated on that schedule are considered evaluable as per the definition in section 3.3 (subject completed at least 2 CC-486 cycles and have undergone the 1st post-baseline tumor burden assessment and the 2nd tumor biopsy). It is critical that data about the tumor biopsies and 1st tumor burden assessment is entered by the sites in the eCRF in a

timely manner since this is required to close accrual for the corresponding cohort also in a timely manner. TRIO will also review the tumor collection and tumor assessments data and closely follow-up the performance of these procedures.

Details regarding the Registration and Enrollment processes are provided in a specific Instruction Manual related to the Registration and Enrollment.

6.1.2.2 Part B

The following steps for registering and randomizing a subject are chronologically performed:

1. The subject must provide written informed consent prior to performing any study specific procedure not considered standard practice by the institution.
2. The site will register the subject in the IWRS system. The registration needs to be done as soon as the subject signs the PICF. The system will uniquely attribute a registration number to each subject in the study and the site will receive an automated registration confirmation.
3. The site will proceed to perform the screening procedures according to the Schedule of Assessments and to sections 6.3 and 6.4. Upon completion of screening procedures the Investigator or his/her delegate will check if the subject meets all eligibility criteria:
 - Subjects who do not meet the eligibility criteria will be moved to a screen failure category in the IWRS.
 - Subjects who meet all eligibility criteria: the sites will enter the screening data in the eCRF which will be reviewed centrally by TRIO. After the review of the eligibility criteria, TRIO may address, if necessary, some discrepancies that will have to be answered by the site. Once the eligibility central review is completed and discrepancies have been resolved (if applicable) TRIO will provide the confirmation that the subject is eligible and the site will be able to move forward with the subject's randomization in IWRS. Treatment assignment will be done by the system and the site will receive an automated randomization confirmation.

Subjects will be randomized to treatment arms in a 1:1 ratio. To ensure the equal distribution of prognostic factors in the two study arms, subjects will be stratified according to the following parameters:

- Type of relapsed disease: platinum-refractory vs. platinum-resistant (refer to the corresponding definitions in section 4.1)
- Prior treatment regimens for the platinum-refractory/resistant EOC: none vs. 1 or 2

Details regarding the Registration and Randomization processes are provided in a specific Instruction Manual related to the Registration and Randomization processes.

Subjects randomized in Part B must start study treatment within 3 days of randomization.

